9.1. CoCoA-PAD Site File

All data will be stored securely using platforms that comply with GDPR, NHS digital governance standards and the Data Protection Act 2018. Other than personal identifiable information, all other research data will be stored on the site file. The site file will be stored using an institutional version of MS SharePoint, with multi-factor authentication log-in procedures, access control, encryption (e.g., password protecting .xlsx files), and a clear audit trail of activity (including tracking file activity and version control history). The site file will include real-time cloud backup and scheduled monthly full project exports into an access-controlled University of Plymouth network drive.

The CoCoA-PAD site file and the CoCoA-PAD database will be created and maintained in compliance with the data quality standards set in the University of Plymouth's Data Quality Policy ([Research Data Policy](#)). The CoCoA-PAD team will ensure that the data is created and maintained following the data quality standards set in. Consideration has been given to the use of open or widely available file-formats and metadata standards that will facilitate the discovery, interpretation and reusability of the data

[figure not shown]

Figure 6. Summary of CoCoA Data Management Plan

9.2. Data Pseudonymisation and Anonymisation

All participants will be assigned a unique, continuous alphanumeric identifier, hereon referred to as the participant ID. Personal information will be stored in a secure database, stored separately to the research database, and only accessible to the CI ([name]), [name], [name], [name], and [name]. The primary research database will not contain any personal or identifiable information and will therefore be fully anonymised. The participant ID will serve as a re-identification key, which links participant's data in the research database to their personal information. The ability to link the participant with their data could be required, for example if a participant requests that their data is withdrawn from the study.

9.3. Data Collection and Processing

The CoCoA-PAD study will involve the collection and processing of a broad range of participant data.

Identifiable personal data

Identifiable personal information will include participants' full names, dates of birth, addresses, general practitioner (GP), and contact details. These identifiers are required for correspondence, safeguarding, and follow-up purposes. This data will be collected at the screening assessment and will be added to a REDCap database that is stored securely and separately from the primary research database. Researchers at the Devon and North East

London sites will have data entry and export permissions on REDCap to upload their participant information data.

Audio Recordings

Although our audio recordings will exclude direct identifiers (e.g. full name, date of birth, NHS number, address), a participant's voice is personal data under the UK GDPR/DPA 2018 because it could indirectly identify an individual. We will not process voices for the purpose of uniquely identifying participants (no voice-print recognition), so the audio is not treated as special-category biometric data under UK GDPR Article 9.

Audio recordings are required to develop speech-based biomarkers for Alzheimer's disease. The research appointment will be recorded, and therefore each participant will provide up to two hours of audio to enable reliable natural language processing and acoustic feature extraction, which in turn supports accurate digital biomarker development. Although a large sample is required, data minimisation is applied: only research-relevant material is recorded, inadvertent identifiers will be redacted during transcription, and access is strictly role-based. Audio is captured on institutionally managed devices via institutional Microsoft Teams accounts (with MFA and SharePoint sync), encrypted at rest and in transit. The University of Birmingham acts as a Data Processor under a formal Article 28 agreement, and analysis is conducted by [name] as an employee of that organisation.

Specific audio data collection procedures are in place for each research site:

- North East London NHS Foundation Trust (NELFT) research team will record sessions on NHS-managed laptops using the Trust's institutional Microsoft Teams accounts (MFA enabled), with automatic syncing to SharePoint.
- Devon Partnership NHS Trust research team will record sessions on NHS-managed laptops using the Trust's institutional Microsoft Teams accounts (MFA enabled), with automatic syncing to SharePoint.
- University of Plymouth / University Hospitals Plymouth NHS Trust site will record sessions on a university-managed laptop using the University's institutional Microsoft Teams account (MFA enabled), with automatic syncing to SharePoint.

All recordings will use the institution's professional Microsoft 365 environment with multi-factor authentication, automatic SharePoint sync and encryption. No consumer devices or personal accounts will be used. These controls ensure audio—treated as potentially identifiable personal data due to the recognisable nature of voice—is captured and stored securely, with access restricted to authorised study personnel only.

Data will be shared with the CI using the SharePoint share function with access control (i.e., only the CI can access it), and an expiration date of 4 weeks. The CI will download the audio file and save it in a separate and secure encrypted folder on SharePoint. The sharing of audio data

will be recorded on REDCap, so that there is a clear audit trail. For data collected at the Plymouth site, this will be recorded directly onto a University of Plymouth MS Teams account and manually transferred to the separate and secure audio recordings folder in the site file.

The MS SharePoint audio data folder will have access-controlled sharing. This data will only be available to the CI, [name], [name], [name], [name], and [name]. The audio data will be accessed by [name], at the University of Birmingham, who are listed as a Data Processor. Given the need complexity of this analysis and the need for multiple analysis pipelines, proportional data minimisation processes will be completed, as outlined previously, and [name] will have access to the raw audio recording files. Audio data will be uploaded to a locally downloaded and run version of Whisper, OpenAI, transcription service. When run locally on a computer, Whisper AI does not upload any data onto a server, and it is GDPR compliant. A transcript of the research session will be produced. Similarly, the audio file will be analysed using code that has been fully developed by [name]. Different types of acoustic and linguistic features will be extracted using Python code that is run locally - the data will not be uploaded to any third-party server at any point. Using those extracted features, a neural network classifier will be trained. The outcome of this classifier will be manually added to the REDCap database.

Demographic and Health Information

Participant demographic and health information will be collected using the Questionnaire feature of Gorilla Experiment Builder. The research sites will be provided with a survey link, with which they can administer the questionnaires and demographic survey to participants. Demographic variables collected will include participants' years of education, socioeconomic status, and relevant health history. Clinical self-report data will be gathered using standardised screening instruments for mood, sleep, and pain.

Gorilla Experiment Builder stores raw data on secure servers, which are only accessible to the primary researcher using their unique multi-factor log-in details. Therefore, only the CI will have access to this data, irrespective of where it was collected. No direct identifiers are stored in Gorilla, and therefore the data are pseudonymised. Raw data will be downloaded onto a Microsoft Excel spreadsheet and manually extracted and transferred into the primary research database on REDCap.

Neuropsychological Assessment Data

Cognitive data will include both quantitative performance-based scores and qualitative observational data derived from neuropsychological tasks. These assessments will be administered digitally using Gorilla Experiment Builder 2.0. All data collection will be conducted electronically; no paper-based data collection methods will be used.

Neuropsychological assessment data collected using Gorilla Experiment Builder will follow an identical process as that outlined in the Demographic and Health Data section. The CoCoA-PAD assessment battery is delivered using Gorilla Experiment Builder, an online behavioural research platform operated by Cauldron Science Ltd. Gorilla is hosted on Microsoft Azure, with

web hosting and data storage located in the EU, specifically the Republic of Ireland. Gorilla is used to present the computerised cognitive tasks and questionnaires, and to collect, store, and export pseudonymised assessment data on behalf of the Data Controllers. Cauldron Science Ltd acts as Data Processor for participant research data collected through Gorilla. UoP acts as the Data Controller. University Hospitals Plymouth NHS Trust, North East London NHS Foundation Trust and Devon Partnership Trust are data processors.

Sensory Screening Data

Sensory screening will be completed using HearWHO and FrACT. These tools will not be used to store direct participant identifiers. HearWHO requires age and gender to generate the screening result, but no other directly identifiable information will be entered. FrACT will be used to generate the relevant visual screening result. Screening outcomes will be entered directly into REDCap by the assessor during the assessment appointment.

MATLAB Structure-from-Motion Task Data

The Structure-from-Motion task will be administered locally on a study laptop using MATLAB. Other than the participants research ID code, no direct participant identifiers will be entered into MATLAB. The task will generate behavioural output, which will be recorded directly into REDCap by the assessor. Where temporary local output files are generated by MATLAB, these will use the participant's pseudonymised study ID only and will be transferred to the approved study storage location or deleted once the relevant REDCap entry has been checked.

CoCoA-PAD Data Processing

In the CoCoA-PAD study, most raw assessment data is automatically within the secure Microsoft Azure environment using embedded analysis pipelines. Outputs from these automated processes are scored within Azure and can be extracted directly through Gorilla's data access platform. Some assessments, however, are not automatically scored and are therefore exported in their raw format. This includes audio recordings, clock drawings, and verbal fluency tasks. These raw files are placed into separate, access-controlled folders in the University of Plymouth SharePoint site file. Authorised researchers at the University of Birmingham (for audio analysis) and Sheffield Hallam University (for clock drawing and verbal fluency analysis) are granted access to these folders. They conduct their analyses, generate derived scores, and return these results to update the research database. Following completion of analysis, both institutions confirm in writing that all working copies of raw data have been deleted at or before study close. Full details of these processes are set out in the Data Management Plan.

- **University of Birmingham (UBham)** will act as a Data Processor for secondary analysis of exported audio recordings and related transcripts and anonymised MRI scans. UBham receives only pseudonymised audio and associated technical metadata (for example, timestamps, task identifiers) via the UoP SharePoint environment. UBham processes these data strictly on the documented instructions of the Controllers, co-ordinated by UoP as lead Controller, and returns only derived speech features to the Controllers. UBham does not receive linkage files or direct participant identifiers.

- **Sheffield Hallam University (SHU)** will act as a Data Processor for secondary analysis of anonymised clock drawings and verbal fluency data. SHU receives only exported clock drawings in raw image format and verbal fluency outputs in raw score format, all pseudonymised and containing no direct identifiers. SHU applies machine-learning and feature extraction methods to generate derived measures, which are returned to the Controllers. SHU processes data strictly on the documented instructions of the Controllers, co-ordinated by UoP as lead Controller, and does not receive linkage files or direct identifiers.

Both institutions act strictly under formal Controller–Processor agreements in accordance with Article 28 of the UK GDPR.

Data Transfers and Access Control. All secondary analyses are supported via a University of Plymouth SharePoint environment with UK data residency. Access is limited to named institutional accounts for authorised staff at UBham and SHU, with mandatory multi-factor authentication. No data are transferred outside the UK. UBham and SHU hold separate, access-controlled copies of data for their analyses within their own secure research environments.

Retention and Deletion. Secondary analysis working copies at UBham and SHU are retained only for the duration required to complete analysis and quality checks. Both institutions will confirm in writing the deletion of their working copies at or before study close in September 2028. The University of Plymouth will retain the raw research dataset in SharePoint for 10 years post-study (until September 2038) in line with sponsor policy.

Compliance and Oversight. Article 28 UK GDPR Controller–Processor agreements are in place with the University of Birmingham and Sheffield Hallam University. Both institutions are contractually bound to maintain confidentiality, apply equivalent security standards to the primary Processor, and notify the Controllers of any personal data breach within 24 hours of

The raw unprocessed CoCoA-PAD data will be stored securely on the site file. In contrast, processed CoCoA-PAD data will be stored anonymously and linked only to the participant identification ID. This data will be available through Gorilla EB2 in .xlsx format and will be transferred to a secure access-controlled folder in the CoCoA-PAD site file. The target data will be manually extracted and transferred into the primary research database on REDCap.

MRI Imaging Data

MRI data are acquired using a Siemens 3T Prisma scanner with a Syngo workstation located at BRIC. After data-acquisition, the MR images are available on the console (directly on the scanner) in DICOM-format. Research data will include whole-head and partial-head MR volumes, T1-weighted hi-resolution volumes, and multi-shell diffusion-weighted images. The MR scanner is operated by a trained Radiographer or Physicist from UHP.

Participant data will be entered manually on the scanner at the start of each participant session. All research acquisitions will use sequences pre-approved by the MR lab heads and

developed in collaboration with the UHP Physicists. All identifying DICOM tags will be filled with non-identifying information. The patient's name with a code. Dob will not be used, only the age of the participant is entered in the system. MR data are, therefore, 'pseudonymised'.

Data are exported using the DICOM protocol to a DICOM server (AET: ORTHANC-Lin2) located on the University of Plymouth's premises and connected to the University network. This server acts as the receptacle for MR data which can then be disseminated across the BRIC Analysis System (AS). This system is delivered, secured, and part managed by Microsoft Azure. The BRIC System Administrator and Lab heads will also have some administrator privileges. MR data will be transferred using the Export function of the scanner Syngo workstation by a trained Radiographer or Physicist. Data transfer will occur at the conclusion of scanning at the end of each day of research.

Data transfer will proceed from the Syngo workstation through the BRIC firewall and via a VPN connection to the Azure environment hosting the DICOM server. The VPN is dedicated only to the transfer of data from the BRIC Syngo workstation to PU and for the transfer of data from PU to Azure and is distinct from the wider PU VPN. Only PU Technology and Information Services (TIS) and BRIC MR lab heads will have access to this VPN, ensuring data cannot be viewed across the PU network.

Data will be subject to filtering (<https://book.orthanc-server.com/users/lu.html#filtering-incoming-dicom-instances>) at transfer to eliminate the possibility of clinical MR data being sent to the PU BRIC Analysis System. A subset of DICOM tags that are present in all clinical scans, but not present in any research scans, will be identified as exclusions for data-transfer acceptance.

At the end of data transfer the Radiographer/Physicist who initiated the transfer, and a MR-lab head or BRIC Systems Administrator, will check the record of transfer on the scanner workstation and on the BRIC Analysis System repository. If clinical data have been found to have been accidentally transferred they will be immediately deleted on the BRIC AS by the MR-lab head or BRIC Systems Administrator and the details will be logged for reporting to the UHPT Clinical Radiography team, UHPT Physics, and Imaging IT [named individuals: [name], [name], [name], [name], [name], [name], [name], [name], [name], [name], [name], [name]]

Data will remain on the scanner until the researcher has confirmed receipt (see below) or one month has elapsed since acquisition.

The DICOM server will be accessed only by the MR lab heads and the BRIC System Administrator. The DICOM server is only accessible via a VNP. Once received by the PU system the DICOM data are converted into the BIDS-format for dissemination to individual researchers. In the course of this conversion, the metadata (DICOM header) relevant to identification of the individual will be separated from the data file and stored separately. The dataset will contain a header and will be accompanied by a json descriptor file and a README file. The BIDS standards provide a simple way of organizing behavioural and neuroimaging data. The increasing

adoption of this format in the community of neuroscientists and psychologists makes data sharing easier.

The BIDS data are made available to named researchers in Neuroimaging Informatics Technology Initiative (NIfTI) format. In order to meet all data protection criteria, all image information of the facial area is removed from structural imaging data prior to its dissemination to researchers.

One copy of the raw data is archived in original DICOM format. Data converted to NIfTI is made available to researchers and students within a managed cloud-based BRIC analysis and storage system. Data are backed up regularly and tiered storage is used to balance cost and accessibility.

The imaging data will be subjected to the following capture and processing pipeline:

Data Acquisition:

- T1 MPRAGE sequence from Alzheimer's Disease Neuroimaging Initiative (ADNI)
- High Resolution T2 (HRT2) of medial temporal lobe sequence from ADNI
- Multishell diffusion sequence from ADNI

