4.1. Study 1. Evaluating the Diagnostic Accuracy of CoCoA-PAD subtests

Participants

A total of 120 participants will be recruited: 60 participants with subjective cognitive decline (SCD) and 60 participants with mild cognitive impairment (MCI). Participants will be classified post-recruitment into four distinct diagnostic groups: healthy controls, preclinical AD, prodromal AD, and non-AD related MCI. Figure 3 provides a flow of the estimated frequencies of each diagnostic group within the sample.

Sampling

This study will use a stratified sampling approach with post-hoc diagnostic classification. A prospective quasi-experimental between-group research design will be employed.

A stratified sampling approach will ensure that key demographic information, including years of education and ethnicity, will match national population demographics of the UK. 2021 census data revealed that 6% of 70–74-year-olds in the UK are from non-white ethnic minority backgrounds. However, given that people from minority ethnic backgrounds are significantly more likely to have dementia but less likely to receive a diagnosis (Okeoghene Ighomereho, 2025), for the purpose of this study, the stratified sampling target will be inflated to 10%.

Similarly, 2021 census data has mapped the educational attainment of the UK population. No age-specific education attainment values were published, but regional values have been published, and Plymouth demographics have been selected for this study. This is based on coastal communities having higher rates of dementia, lower rates of diagnosis, and significant social inequalities which often exclude them from research (Alzheimer’s Research UK, 2024). This study will replicate educational attainment values, with provision for 5% variation in the recruitment to each education level – see Table 1.

Table 1. Educational Attainment and Stratified Sampling Target

Educational Attainment	Plymouth Demographics	CoCoA-PAD Recruitment Target Range
No Qualification	17%	14-26
Level 1 (O level any grade)	10%	6-18
Level 2 (O levels passes)	14%	11-23
Apprenticeship	6%	1-13
Level 3 (A level equivalent)	17%	14-26
Level 4 (3 rd level qualifications)	34%	35-47
Other	2%	0-8

Procedure

Participants will be recruited and classified post-recruitment into diagnostic groups on the basis of AD biomarker results (pTau-217) and performance on the M-ACE, using a cut-off score of 20 for MCI (Potts et al., 2022).

Measures

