6.5. Informed Consent

All research appointments at the Plymouth site will take place at the Brain Research and Imaging Centre (BRIC). Data collection at the Devon and North East London sites will be conducted by local NHS research teams in NHS clinical settings. The environment will be quiet and distraction free. At the beginning of the session the investigator will read through the relevant information sheet with the participant and answer any questions. For participants with a mild cognitive impairment, a mental capacity assessment will be completed again. For participants who demonstrate mental capacity to participate, and who indicate their willingness to do so, they will be asked to review the electronic consent form (see Electronic Consent Form).

Informed consent will be documented using the REDCap secure electronic data capture system, hosted on University of Plymouth servers. The consent form will display version and date control, and the wording is identical to the Electronic Consent Form attachment. Participants will be required to tick each statement. An electronic signature will be collected using a finger or stylus signature and stored securely in the REDCap database. An audit trail will record the date and time and identity of the consenting individual. The process allows participants to ask questions before completing consent, ensuring compliance with the Joint statement on seeking consent by electronic methods ([hra-mhra-econsent-statement-sept-18.pdf](https://www.hra-nhs.uk/consult/ia/pdfs/hra-mhra-econsent-statement-sept-18.pdf))

At the point of consent, participants will be asked whether they wish their General Practitioner (GP) to be informed of their participation in this research. This is optional and will not affect eligibility or clinical care. Where a participant provides explicit consent, a brief notification letter will be emailed to their GP at the time of consent, confirming study participation and outlining that the research is observational, does not alter routine care, and that no clinical results will be returned. No notification will be sent without the participant's explicit consent.

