6.6. Data Collection

Participation at the Plymouth site includes the completion of demographic and health screening questionnaires (10 minutes), a 2-hour cognitive assessment, which includes a 10-minute break, a blood test by a trained NHS research nurse or phlebotomist (5 minutes), and an MRI scan (30

minutes). In total, the appointment is estimated to last approximately 2 hours 45 minutes. Participation at the Devon and North East London sites will be similar, but without the MRI scan, and therefore it will take approximately 2 hours 15 minutes. The assessment will follow the flow outlined below. However, on occasion when the MRI scan is unavailable immediately after the appointment, or if the participant indicates they are too fatigued, the participant may be asked to return for a separate appointment to complete the MRI imaging.

- Review Information Sheet
- Sign Consent Form
- Collect Demographic Information (age, gender, education etc)
- Collect Health History Information (e.g., comorbidity, sensory difficulties)
- Screening Health Questionnaires: PHQ-2, GAD-2, ISI and NRS
- Disease Severity Screening: SCD-Q9 and M-ACE
- Sensory screening (hearing, visual acuity and visual contrast sensitivity)
- CoCoA-PAD Assessment (Gorilla EB2 and MATLAB)
- Blood Test
- MRI Scan (only for participants at the Plymouth site)
- De-brief

This is a long appointment, and it may pose barriers for some participants' engagement due to fatigue, stress or medical issues. Firstly, all participants will receive breaks after every 40 minutes of research activity. Breaks are scheduled for a minimum of five minutes, with longer breaks supported, if needed. Participants will be informed in the consenting process that they can request additional breaks, also. Given that some participants may minimise discomfort, fatigue or distress, the assessor will routinely ask participants whether they are experiencing signs of fatigue, headache, brain fog, and pain. If the participant discloses this, the assessor will offer an additional break and use their clinical judgement on whether continuing the appointment is appropriate.

For participants who are unable to complete the assessment in a single appointment, they can request that the appointment is delivered over two sessions instead. These appointments would be scheduled approximately 1 week apart.

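### Section 9.3 trains the speech classifier on audio of the research appointment without excluding the M-ACE, which helps assign the diagnostic groups, so contrasts across the M-ACE cut-off are open to incorporation bias

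*Protocol*

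**What the plan says.** **What is recorded.** Protocol section 9.3 (Audio Recordings) states: "The research appointment will be recorded, and therefore each participant will provide up to two hours of audio". It gives the purpose as developing speech-based biomarkers, and justifies the length by the needs of language processing and acoustic feature extraction. The one stated limit on content is that "only research-relevant material is recorded".

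**What is done with it.** Section 9.3 continues: "A transcript of the research session will be produced", and then, after feature extraction, "Using those extracted features, a neural network classifier will be trained". The classifier's output is entered in REDCap. The section names neither the segments of the recording that are used nor the label on which the classifier is trained.

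**What else happens at the appointment.** The list in section 6.6 includes "Disease Severity Screening: SCD-Q9 and M-ACE" ahead of the CoCoA-PAD battery.

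**How groups are formed.** Section 4.1 classifies participants "on the basis of AD biomarker results (pTau-217) and performance on the M-ACE, using a cut-off score of 20 for MCI"; section 4.6 repeats this.

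**What the speech subtest is.** Appendix 1 describes Connected Speech as a 5-minute task of its own. Appendix 2 gives it an exploratory, non-primary diagnostic hypothesis.

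**The concern.** In a diagnostic accuracy study the index test should not draw on the reference standard. Here the M-ACE is half of the reference standard, and its spoken administration falls within the appointment whose audio and transcript feed the speech classifier. The M-ACE tests attention, memory, fluency and visuospatial ability (section 6.2), so a session transcript could carry much of its content. A classifier given that material can recover M-ACE performance directly, and M-ACE performance decides which side of the MCI line a participant falls on.

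At stake is how a speech accuracy figure for prodromal AD versus healthy controls can be read, which is the contrast in primary objective ii. Part of that figure could be the M-ACE result read back from the recording. That part would not carry over to a setting where only a speech task is recorded. Section 9.3 also does not say how a measure built on session audio relates to the 5-minute subtest in Appendix 1.

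**Working it through.** **1. Does the audio appear to be whole sessions?** Section 9.4 gives 60–100 MB per file and a folder of 7.2–12 GB; section 4.1 gives 120 participants.
- 120 × 60 MB = 7.2 GB and 120 × 100 MB = 12 GB. The stated total reproduces exactly with one file per participant.
- Bit rate = MB × 8,000 / seconds. Over 120 minutes (7,200 s): 60 × 8,000 / 7,200 = 67 kbps and 100 × 8,000 / 7,200 = 111 kbps. Over 5 minutes (300 s): 1,600 and 2,667 kbps.
- The sizes suit session-length audio better than 5-minute clips. This is supporting evidence only, since the files are mp4 and the encoding is not stated.

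**2. Does the M-ACE fit in the two-hour block?** Section 6.6 gives 120 minutes of cognitive assessment including a 10-minute break. CoCoA-PAD takes 90 minutes by section 6.2. The Appendix 1 times sum to 4+15+15+15+5+2+10+4+3+6+5+5+5+4 = 98 minutes.
- Remaining time: 120 − 10 − 90 = 20 minutes, or 120 − 10 − 98 = 12 minutes.
- The M-ACE takes 5–10 minutes (section 6.2), so it fits.

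**3. Shares of two hours of audio.** Connected Speech: 5/120 = 4%. M-ACE: 5/120 to 10/120 = 4–8%. The M-ACE supplies at least as much audio as the speech subtest. These are shares of time, not effect sizes.

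**4. Which contrasts can be affected?**

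| Contrast | M-ACE cut-off crossed? | Separated by |
|---|---|---|
| Prodromal AD vs healthy (primary ii) | Yes | M-ACE and pTau-217 |
| Preclinical AD vs healthy (primary i) | No | pTau-217 |
| Prodromal AD vs non-AD MCI (secondary iii) | No | pTau-217 |

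Section 4.6 keeps Study 1 data collection blind to biomarker status. That protects the pTau-217 split but does nothing about the M-ACE.

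**5. Illustration of direction, on assumptions that are not in the protocol.** Let the M-ACE be standard normal and split at its median. Let pTau-217 be independent of it. Let a speech feature carry no information except a correlation ρ with the M-ACE. Then, for prodromal AD versus healthy controls,

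AUC = 1/2 + (2/π) · arcsin(ρ/√2).

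| ρ | 0 | 0.2 | 0.4 | 0.6 | 0.8 | 1.0 |
|---|---|---|---|---|---|---|
| AUC | 0.50 | 0.59 | 0.68 | 0.78 | 0.88 | 1.00 |

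A simulation of the same model agrees to within 0.01, and gives about 0.50 for preclinical AD versus healthy controls at every ρ. The protocol gives no value for ρ, so none of these figures estimates the bias in this study.

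**The case against.** The strongest reply is that section 9.3 leaves the choice of segments open. It does not say that the M-ACE is fed to the classifier, and it sends timestamps and task identifiers with the audio, so task-level clipping is possible. It refers to a Data Management Plan for detail, and section 11.4 calls the analysis plan provisional. This stands to the extent that contamination is a route the text permits, not something shown to occur. It does not dispose of the point. Section 9.3 itself names the session recording as the input, no section excludes the M-ACE, and the M-ACE is plainly research-relevant.

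A second reply is that the speech biomarkers are a separate development strand. Section 7.9 lists their intellectual property apart from CoCoA-PAD, and Connected Speech is exploratory. This also stands: it limits the importance of the point and argues against cutting all the audio down to the speech tasks, given the stated need for a large amount of it.

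A reader might infer more than the documents support:
- **That the whole visit is recorded.** The visit lasts 2 h 15 to 2 h 45, while the recording is up to two hours, so consent and health history may fall outside it.
- **That talk specific to MCI recruits reveals the group.** Section 6.5 does say "For participants with a mild cognitive impairment, a mental capacity assessment will be completed again". But sections 7.2 and 10.5 describe a similar teach-back or capacity check for participants generally. It precedes signed consent, and nothing says it is recorded.
- **That the SCD-Q9 leaks the reference standard.** It plays no part in group assignment, and for recruits from outside PROTECT who enter on screening scores the same threshold applies in both strata.
- **That the main subtest results are compromised.** The route concerns only the speech classifier.

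**Conclusion.** The point holds as a gap in section 9.3. Following the text as written places part of the reference standard inside the input to the speech classifier. Its accuracy for prodromal AD versus healthy controls, or for any other contrast across the M-ACE cut-off, would then be open to incorporation bias. Preclinical AD versus healthy controls and prodromal AD versus non-AD MCI are not directly affected.

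The size of any inflation cannot be derived from the protocol, because the segments used, the training label and the classifier's dependence on M-ACE content are not given. The conclusion assumes that the M-ACE falls within the recorded period, which the time budget supports but the protocol does not state outright. Since the measure is exploratory and the other subtests are untouched, this is an inexpensive improvement and not a threat to the primary analyses.

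**What to change.** In section 9.3:
1. State that the M-ACE segment, and any consent or capacity conversation that happens to be recorded, is removed before feature extraction and classifier training, using the timestamps and task identifiers already supplied with the audio.
2. State that any result reported for the Connected Speech subtest uses only the audio of that task as defined in Appendix 1.
3. State that any model built on the wider session audio is reported separately, as speech-biomarker development.

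The cost is about 5–10 minutes less audio per participant for the session model, some clipping work, and matching wording in the Data Management Plan. The remaining session audio stays available, so the stated need for a large sample of speech is largely met, and the change fits the protocol's own data-minimisation aim.
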